Diabetes represents one of the largest documented health disparities between Latinos and non-Latino whites²³ and Latinos often receive suboptimal treatment. For example, Latinos are less likely than whites to receive appropriate HbA1c and lipid screening^{24, 25} and are less likely to achieve treatment goals, including glycemic, cholesterol, and blood pressure control²⁶⁻²⁹. Since Latinos, African-Americans, and certain Asian sub-groups are more likely to have diabetes compared to whites, many studies have focused on developing and testing interventions to improve outcomes of diabetes care through patient activation and engagement among these vulnerable patient populations³⁰⁻³³. ACOs can play an important role in implementing PA&E initiatives that span clinical and community settings, including community health worker or health coach models for diabetes care management. The care of patients with diabetes and CVD presents many challenges for health care delivery systems³⁴. Knowledge is emerging on how to better care for patients with these conditions, but little is known about how patients can be better activated and engaged in their own care and what health care providers and care teams can do to promote such engagement and with what results. This proposal directly addresses these issues.

B. Significance

CRITERION 2 – ATTEMPTS TO IMPROVE HEALTH CARE AND OUTCOMES

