We will collect patient demographic information as part of the patient surveys, including patient age, sex, race, ethnicity, self-rated English proficiency, preferred language, interpreter use, employment status, marital status, education, and military status. We will supplement these survey data with information about patient age and sex from ACO clinical and sociodemographic data submitted to Berkeley as part of the project.

TEAMWORK ASSESSMENT INSTRUMENTS

Primary care team members from each of the 16 practices will complete the following instruments that we refer to as "teamwork assessment instruments." These are: (1) team culture, (2) team leadership, (3) relational coordination, and (4) perceived team effectiveness. These will be completed at baseline (0-3 months) and then again at 18 months.

Implementation of the teamwork assessments will be overseen by a data coordinator at each ACO paid in part by the grant.

An important component of the project is to provide primary care teams and patient advisory groups with feedback on their patient's reports of physical functioning, social functioning, and experiences of primary care. As primary care practices embark on integrating new roles and responsibilities for non-physician clinicians and staff for improving patient activation and engagement, supportive practice environments that foster organizational learning and effective teamwork are essential.^{63, 64} Providing primary care teams with performance feedback on patient-reported outcomes, patient experience, and clinical quality of care measures is one important way of fostering a shared responsibility for patient care among interdisciplinary members^{65, 66} and supporting a measured approach to team performance improvement efforts.⁶⁷ When teams do not receive feedback on their collective work, members often encounter difficulties working together to modify existing workflows and procedures^{68, 69}. Consequently, team feedback on patient experience and PRO data and teamwork assessment can aid primary care teams in their process improvement efforts. The limited amount of performance feedback available to primary care teams on their patients' experiences and patient-reported outcome measures⁷⁰ can have important downstream consequences for patient care, including less patient-centered clinician-patient communication and self-management support.

PRINCIPAL INVESTIGATOR (LAST, FIRST, MIDDLE): [name]

Team Composition Assessment

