Analyses Addressing Aim 1. At each of the two cross-sections for the patient and teamwork assessment surveys, we will clean the data, examine their distributions, and conduct psychometric analysis to assess the reliability and validity of the measures. After composite variables have been constructed and properties assessed, we will examine the cross-sectional relation of PA&E activities, teamwork assessment results, and patient survey results. Using a dichotomized variable derived from baseline responses to the PA&E Practice Site Assessment Survey (see Appendix I), we will categorize sites as “high” or “low” PA&E based on the response distributions in our data. We will then assess association of key measures in two stages. In the first equation, using linear regression models, we will examine the PAM as a function of high vs. low PA&E (site level), controlling for practice size, and for patient casemix adjustment variables previously used in research that has compared organizations on patient experience and clinical quality measures^{79, 80}. Casemix factors to be considered include age, sex, educational attainment, and comorbid health conditions. We will then examine the patient reported outcome (PRO) measures, patient experience (PE) and the clinical measures as a function of the PAM, PA&E level (at site level), practice size, and casemix using multilevel regression models to account for the clustering of patients within practices. The simplified equations are:

$$PAM = Hi / lowPA \& E + PracticeSize + Casemix + \epsilon$$

$$PE = Hi / lowPA \& E + PAM + PracticeSize + Casemix + \epsilon$$

$$PRO = Hi / lowPA \& E + PAM + PracticeSize + Casemix + \epsilon$$

$$ClinMeasures = Hi / lowPA \& E + PAM + PracticeSize + Casemix + \epsilon$$

Aim 2. To assess whether the relation of PA&E activities and better PROs and clinical outcomes is stronger for more highly activated patients than less activated patients at baseline.

Analyses Addressing Aim 2. To address the extent to which PA&E activities conducted by the practice are more influential in improving PROs and patient experience among patients with high PAM levels at baseline, we will extend the Aim 1 analyses. Specifically, we will use multilevel regression with site random effects to model changes in PROs and the clinical measures over time as a function of baseline PAM scores, practice size, patient casemix, PA&E, and then by interacting PA&E and the PAM scores. The simplified equations are:

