From among those practices we will select 273 patients with diabetes and/or CVD from each of eight practices at each ACO – a total of four practices with high involvement in PA&E and four practices with low PA&E involvement. Given two ACOs, we will have data from 4,368 patients with these chronic conditions. We will follow them as cohorts over a two-year period. We will obtain measures of blood pressure, HbA1c and LDL-C at 12 months and 24 months from the EHR. Patients selected for the study will be mailed a survey including the 13-item PAM measure at baseline (0-3 months). Patients will complete patient-reported outcomes (PROMIS) and experience of care measures between 7-12 months and again at between 19-24 months. Patients who do not complete and return the survey by mail will be contacted by phone (up to 8 attempts) and offered an opportunity to complete the questions by computer-assisted telephone interview (CATI). We will survey and follow-up with patients in both English and Spanish, according to their stated primary language preference. Patients will be offered a \$20 incentive to complete the survey by mail or by CATI. The calculations provided below for the PROMIS self-reported measures and for blood pressure provide evidence of sufficient statistical power to detect meaningful differences between practices on these key variables of interest.

To project the sample size requirements given 16 practices (8 high PA&E and 8 low PA&E), we estimated the design effect (DE) to account for the clustering of patients within practice sites. While PROMIS data from participating ACO patients are presently unavailable, recent studies of change over time on the PROMIS physical functioning measure informed our sample size estimates for the PROMIS measure⁴⁷. Having been selected using item-response theory (IRT) methods and extensive testing, the PROMIS physical functioning measure is a precise measure that is sensitive to small changes in physical functioning over time.

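### The Aim 1 adjustment names no race/ethnicity, language or ACO term, although the contrast is not randomised and the protocol ties ethnicity to its clinical outcomes

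*Combined protocol and SAP*

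**What the plan says.** All references are to the combined protocol and SAP.

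- **Adjustment set (Analysis Section, Aim 1).** The models control for practice size and for "patient casemix adjustment variables previously used in research that has compared organizations on patient experience and clinical quality measures". The plan then adds: "Casemix factors to be considered include age, sex, educational attainment, and comorbid health conditions". No equation under Aims 1 to 5 names race/ethnicity, language or ACO. The Aim 4 equations show only the changes in PA&E and PAM, with casemix and practice size left to be examined.
- **What is collected (Measures, Patient Demographics).** The patient survey asks for "race, ethnicity, self-rated English proficiency, preferred language, interpreter use, employment status, marital status, education, and military status", besides age and sex. For data from the ACOs, the same section says: "We will supplement these survey data with information about patient age and sex from ACO clinical and sociodemographic data".
- **Link to outcomes (Criterion 1).** Latinos "are less likely to achieve treatment goals, including glycemic, cholesterol, and blood pressure control". Blood pressure, HbA1c and LDL-C are the study's clinical measures.
- **Exposure (Clinic/Practice Selection; Measurement of Site PA&E Activities).** Practices are ranked on existing PA&E activity. Four are drawn from the top quartile and four from the bottom quartile in each ACO. Under Aim 1, the high/low label is set again from the baseline site survey responses, and the four-and-four split by ACO is not restated.
- **Patient mix (Table 2).** One ACO is 55% Latino and the other 8%.
- **Survey conduct (Protection of Human Subjects, UC Berkeley).** "We will survey and follow-up with patients in both English and Spanish, according to their stated primary language preference". Patients who do not return the mailed form are followed up by telephone.

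**The concern.** Nothing in the design makes the patients of high and low PA&E practices alike, so the Aim 1 contrast is only as good as its covariates. A variable belongs in the planned set if it relates to the outcome, can plausibly differ between the two groups of practices, and is already collected. By the protocol's own account, ethnicity meets the first and third conditions for the clinical measures. The second is plausible, because practices within an ACO serve different communities. Language is collected and is closely related to ethnicity.

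If the two groups of practices differ in this mix and the models ignore it, part of the difference will be read as an effect of PA&E. Aim 1 is cross-sectional, so a difference in outcome level enters the estimate directly. Because the list is only of factors to be considered, the final covariates could also be chosen after results are known.

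**Working it through.** **Step 1. Reproduce the plan's own figures.**

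- Patients with two surveys: 4,368 × 0.97 × 0.50 × 0.65 × 0.80 = 1,101.6, or 68.9 per practice. The plan states 1,102 and 69.
- Planned Hispanic count: (0.08 + 0.55)/2 × 4,368 = 1,375.9. The enrolment table gives 702 + 674 = 1,376. The enrolment plan therefore uses the 8% and 55% shares with equal numbers from each ACO.

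**Step 2. The between-ACO part.** Let h of the 8 high practices come from the 55% ACO, with 8 high and 8 low practices of equal sample size and each practice at its ACO's average. The high-minus-low difference in Latino share is (2h − 8)/8 × 47 points.

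| h | Difference in Latino share (points) |
|---|---|
| 4 | 0 |
| 5 | 11.75 |
| 6 | 23.5 |
| 8 | 47 |

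Under the planned selection (h = 4) the gap between ACOs contributes nothing. It returns only if relabelling changes the split.

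**Step 3. The within-ACO part.** The documents give no practice-level shares, so this is an assumption. Suppose Latino share varies across practices in the 55% ACO with an SD of 20 points. A four-versus-four difference there has a standard error of 20 × √(1/4 + 1/4) = 14.1 points. Averaged over both ACOs, with the other adding little, that is about 7 points. Imbalances of 5 to 10 points could thus arise by chance.

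An imbalance of 20 points is an upper end. If the selected practices in the 8% ACO average 8%, their difference is at most 16 points (16% against 0%), so the other ACO would need 2 × 20 − 16 = 24 points. With the 8% ACO balanced, it would need 40.

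**Step 4. Illustrative bias.** Bias = (difference in Latino share) × (outcome gap that remains after the named covariates). The documents give no gap, so 1, 3 and 5 mm Hg are assumed.

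| Imbalance | 1 mm Hg | 3 mm Hg | 5 mm Hg |
|---|---|---|---|
| 5 points | 0.05 | 0.15 | 0.25 |
| 10 points | 0.10 | 0.30 | 0.50 |
| 20 points | 0.20 | 0.60 | 1.00 |

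The largest value is one third of the 3 mm Hg target (Patient Selection). That target is a difference in change, whereas Aim 1 compares levels, so it serves here only as a yardstick.

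**Step 5. Can the adjustment be made?** The Aim 1 clinical models include PAM, a survey measure, so they are already limited to survey respondents, who are the patients asked about ethnicity and language. About 4,368 × 0.97 × 0.50 = 2,118 are expected at wave 1. Adding the covariates changes no stated sample size, apart from any item non-response.

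**The case against.** The strongest reply is that the list is open. It names factors to be considered, and it points to earlier research whose covariates cannot be seen here. A reader might infer that the plan rules these variables out; the documents show only that they are not pre-specified. That narrows the point but does not remove it, since the plan commits to nothing on variables that it already collects.

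Three further inferences are tempting and are not supported.

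- **That the 55% against 8% gap itself confounds the contrast.** Selecting four high and four low practices in each ACO cancels it while that balance holds.
- **That the protocol ties all of these variables to all outcomes.** The stated link is between ethnicity and screening and control of the clinical measures. No outcome is linked to language, and no ethnic gap is stated for PROMIS or patient experience. A bias expressed as a share of the 0.20 SD PROMIS difference therefore has no basis in the documents.
- **That survey mode belongs in the main adjustment.** The plan does not say that mode is kept as a variable. Its only tie to outcomes is the title of one cited reference. Telephone goes to those who did not answer by mail, so mode arises after exposure and may itself reflect activation; adjusting for it could introduce bias. It cannot affect the EHR measures.

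It is also fair to say that Aims 2 and 4 model change, where a stable difference in level by ethnicity largely cancels. Only different change over time would bias those estimates.

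**Conclusion.** The point stands in limited form. The Aim 1 contrast is not randomised, its named covariates omit race/ethnicity and language, and the models have no ACO term, although the protocol collects the first two and itself ties ethnicity to the clinical outcomes. The practice selection deals with the difference between ACOs only if relabelling preserves it, and it does not balance practices within an ACO.

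The size of any bias cannot be found from the documents. The range of 0.05 to 1.0 mm Hg rests wholly on an assumed imbalance of 5 to 20 points and an assumed residual gap of 1 to 5 mm Hg; it could also be zero. For Aims 2 and 4 it should be smaller. This is a cheap improvement, not a fault that undermines the study.

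**What to change.** 1. Name race/ethnicity and preferred language or English proficiency as casemix covariates in the Aim 1 models, fixed before outcomes are examined.
2. Add an ACO term to the Aim 1 models. It matches the way practices are selected and removes the between-ACO part if relabelling breaks the four-and-four split.
3. Carry the same terms into the Aim 2 and Aim 4 models, where less bias is expected.
4. Report the high-versus-low estimate with and without race/ethnicity.
5. Keep survey mode out of the main adjustment. Record how each survey was completed, and use it only in a sensitivity analysis of the survey outcomes.

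**Cost.** A few patient-level parameters against roughly 2,118 wave 1 respondents, and one extra table. The ACO term takes one practice-level degree of freedom: with an intercept, the high/low term and a single term for practice size, 16 − 3 = 13 become 16 − 4 = 12. Some readers object to adjusting for race; showing both estimates lets them judge whether the conclusion depends on it.

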It is increasingly obvious that to improve patient outcomes and experience of care will require enhanced PA&E³⁵. There is a small but growing literature suggesting that more activated patients experience better health outcomes³⁶⁻⁴⁰. But much less is known about how to accomplish this^{41, 42}. For example, national data on trends between 2008 and 2012 indicate essentially no change in the percentage of patients with blood pressure under 140/90, the percentage of heart care patients with LDL-C < 100, the percentage of diabetes care patients with LDL-C < 100, and the percentage of patients with diabetes who have blood pressure under 130/80 and HbA1c under 9 percent⁴³. We recognize that for patients with diabetes over age 85 that strict adherence to these numbers is controversial and therefore we will exclude patients over 85 from this study.^{44, 45} In addition, almost no systematic data are available on patient-reported outcomes of care in terms of physical and social functioning and related dimensions. Patients often struggle to live their lives while adhering to multiple medications, experiencing side effects, and trying to change behaviors such as smoking, diet, and physical activity. The results from this research will provide important knowledge and guidance for others, particularly in regard

PRINCIPAL INVESTIGATOR (LAST, FIRST, MIDDLE): [name]

to what health care organizations and teams might do to strengthen their PA&E efforts and the impact on measures of most interest to patients.

SPECIFIC AIMS

Based on the above discussion, the specific aims of the study are outlined below:

- 1) To answer the question: Do patients with diabetes and CVD receiving care from practices with higher versus lower PA&E activities have better patient-reported outcomes (PRO) of care, patient experience, and clinical outcomes?
- 2) To answer the question: Is the relationship of PA&E activities and improved PROs stronger for more highly activated patients than for less activated patients at baseline?
- 3) To assess the stability of the PA&E-outcome relationship over two measurement periods at the individual- and practice-level.
- 4) To assess changes over time in patient-reported outcomes of care, patient experience, and clinical measures, as a function of changes over time in PA&E activities and patient activation.

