We posit that practices that have more highly developed PA&E and better teamwork will more effectively activate patients with diabetes and/or CVD. In turn, we posit that more highly activated patients will be more likely to achieve improvements on patient-reported outcomes, patient care experiences, and clinical measures over time compared to less activated patients. We also will also examine the roles that patient advisory groups and primary care team use of performance feedback data play in influencing improvements in patient activation and outcomes of care over time.

Figure 1. Logic Model

We will engage patients and primary care practice teams within two accountable care organizations (ACOs). In each ACO, we will randomly select eight practices: four who score high on PA&E activities and four who score low. We will survey practice team members twice: once at baseline and one a year later. We will also conduct two site visits: one near the beginning of the study and one during the 13-18 month period of the study.

[figure not shown]
We will randomly select four high and four low PA&E sites within each ACO using a broad definition of PA&E activities including: (1) patient care outreach in regard to disease prevention and health promotion; (2) changes in the clinician-patient relationship, particularly in the areas of communication, motivational interviewing, and patient involvement in treatment care plans; (3) shared decision-making; (4) patient self-management of their condition(s); (5) end of life/advanced serious illness care patient engagement and family involvement; and (6) patient involvement in the overall design of care and in organization-wide efforts to improve the quality of care. See methods section for a description and Appendix I for an example of the instrument to be used for determining the “more highly involved” and “less highly involved” practices.

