Patient Reported Outcome Measure – PACIC-11

The Patient Assessment of Chronic Illness Care scale (PACIC-11) developed and validated by Glasgow et al⁵⁸ (Medical Care, 2005; see Appendix II) will be used to assess the extent to which practices engaging in more PA&E activities and with higher team functioning will be able to effectively improve patients' experiences of chronic illness care over time. The PACIC-11 has high Cronbach's alpha internal consistency, reliability of 0.93, and reasonable test-retest reliability of 0.58. It also demonstrates convergent validity with the Hibbard PAM measure and several dimensions of the Ambulatory Care Experiences Survey (ACES), the precursor to the Clinician Group Consumer Assessment of Healthcare Providers and Systems (CG-CAHPS) survey ([name] and Crane 2011)⁵⁹. We will supplement the PACIC-11 with selected items from the Ambulatory Care Experiences Survey (ACES) focused on patients' experiences of primary care teams ([name], Rogers et al., 2007)⁶⁰. (See Appendix II)

Clinical Measures

Based on each site's EHR, we will have de-identified data for blood pressure, lipids, and HbA1c to measure percentage of hypertensive patients with blood pressure controlled (<140/90 mm Hg), percentage of patients with diabetes with blood sugar controlled (HbA1c <8.0%), and percentage of patients with cardiovascular conditions or diabetes whose lipids are controlled (LDL-C <100 mg/dL). The patient survey sampling frame includes "established" patients of each primary care physician and team. The adult diabetic and CVD patients will need to have at least two primary care visits in the baseline year (2013) to improve the reliability of reports of patients' experiences of care and to focus on an established patient population that has a high propensity to maintain clinical relationships and receive routine primary care over time. Since attribution of patients to practices and PCPs is a contentious issue in performance measurement in improvement^{61, 62}, restricting the sample to patients with diabetes and/or CVD who have ongoing relationships will also aid in team acceptance of the feedback data.

Patient Demographics

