$$PE = Hi / lowPA \& E + PracticeSize + PAM + PA \& E * PAM + Casemix + \epsilon$$

$$PRO = Hi / lowPA \& E + PracticeSize + PAM + PA \& E * PAM + Casemix + \epsilon$$

$$ClinMeasures = Hi / lowPA \& E + PracticeSize + PAM + PA \& E * PAM + Casemix + \epsilon$$

We will explore differences between the two extreme PAM categories (level 1=lowest activation, 4=highest activation) in addition to examining the continuous PAM measures, as we expect the biggest differences over time differences in PRO and patient experience between patients with highest and lowest baseline PAM scores.

PRINCIPAL INVESTIGATOR (LAST, FIRST, MIDDLE): [name]

Aim 3. To assess the stability of the PA&E-outcome relationship over two measurement periods at the individual and practice-level;

Analyses addressing Aim 3. After both waves of data collection are completed, we will assess the consistency of the results at two levels- patient-level and practice-level. We will compare the regression coefficients for models at each wave to examine differences in associations of the independent variables with outcomes at each cross-section.

Aim 4. To assess changes over time (T1 vs. T2) in patient-reported outcomes of care, patient experience and clinical measures, as a function of changes over time in PA&E activities, patient activation, controlling for patient casemix.

Analyses Addressing Aim 4. We will integrate the patient survey results and the patient level results at the practice level. We will examine 'over time' effects using three approaches: 1) multilevel regression with interaction term as specified here, 2) stratified by low vs. high PA&E practices and looking at coefficient differences, 3) lagged regression (using T1 to predict T2) vs. change in T1 and T2 predicting T2), etc. The simplified equations below provide a multilevel framework for studying the impact of site PA&E activities on patient activation, patients' experiences, and patient-reported outcomes over time:

$$\Delta PRO = \Delta PA \& E + \Delta PAM + \varepsilon$$

$$\Delta PE = \Delta PA \& E + \Delta PAM + \varepsilon$$

$$\Delta ClinMeasures = \Delta PA \& E + \Delta PAM + \varepsilon$$

Given the uncertainty in distribution and variation, we will examine the inclusion of other relevant predictors including fixed effects for casemix and practice size.

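### All Aim 1 outcome models adjust for PAM, which the plan itself treats as a consequence of PA&E, so none estimates the overall high-versus-low contrast that Aim 1 asks for

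*Combined protocol and SAP*

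**What the plan says.** The first Specific Aim is a plain group comparison: "Do patients with diabetes and CVD receiving care from practices with higher versus lower PA&E activities have better patient-reported outcomes (PRO) of care", and likewise for patient experience and clinical outcomes. Nothing in that question conditions on activation.

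The Research Plan sets out the assumed mechanism in two steps. First, "We posit that practices that have more highly developed PA&E and better teamwork will more effectively activate patients with diabetes and/or CVD". Second, "we posit that more highly activated patients will be more likely to achieve improvements on patient-reported outcomes", along with care experience and clinical measures. Activation is therefore an intermediate step between PA&E and outcome.

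Analyses Addressing Aim 1 announces: "We will then assess association of key measures in two stages". Stage one has PAM as the dependent variable, with high/low PA&E, practice size and casemix as predictors. Stage two examines patient-reported outcomes, patient experience and "the clinical measures as a function of the PAM, PA&E level (at site level), practice size, and casemix using multilevel regression models". The three displayed outcome equations (PE, PRO, ClinMeasures) match this sentence: each contains both high/low PA&E and PAM.

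The displayed Aim 2 outcome equations contain PAM and its interaction with PA&E. The Aim 4 equations contain change in PAM, in line with the stated aim of modelling outcome change "as a function of changes over time in PA&E activities, patient activation, controlling for patient casemix".

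**The concern.** When a regression includes a variable that lies between exposure and outcome, the exposure coefficient loses the part of the association that runs through it. Here that part is the mechanism the study was set up to examine. If high-PA&E practices raise PAM, and higher PAM goes with better outcomes, the reported PA&E coefficient lies below the overall contrast. The more fully activation explains the benefit, the closer the coefficient gets to zero. A small or null estimate could then be reported as high-PA&E practices doing no better, although the overall difference is real.

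There is a second problem. Health status or mood could affect both PAM and the outcome, and the main text collects PAM in the same survey as the patient-reported outcomes. Conditioning on PAM then brings in bias of unknown sign. Aim 3, which compares coefficients between waves, inherits both problems if it reuses these models.

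**Working it through.** **1. Is there a PAM-free outcome model anywhere?**

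| Place | Dependent variable | PAM on the right-hand side? |
|---|---|---|
| Aim 1, stage one | PAM | it is the outcome |
| Aim 1, stage two (text and three equations) | PE, PRO, clinical | yes |
| Aim 2 (three equations) | PE, PRO, clinical | yes, with interaction |
| Aim 4 (three equations) | change in PE, PRO, clinical | yes, as change |

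No outcome model omits PAM, and no step adds the path through PAM back in.

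**2. What the Aim 1 coefficient estimates.** For linear models on the same patients and covariates, total = direct + a·b, where a is the PA&E effect on PAM and b the PAM slope for the outcome. Stage two reports the direct term. If a share s of the total runs through PAM, and PAM has reliability λ, then without confounding

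adjusted / total = 1 − s·λ.

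**3. Size.** Inputs from the documents:

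- Reliability is 0.79 to 0.82 in the Patient Activation (PAM) section, so λ = 0.8. Appendix II gives 0.90 or more, so λ = 0.9 is also shown.
- Power is 0.90, two-sided, in Patient Selection. It is stated only for change in systolic pressure and is borrowed here for illustration.

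Assumed: alpha 0.05, unchanged standard error, no PAM-outcome confounding, and s over a range. The total contrast then sits at 1.960 + 1.282 = 3.242 standard errors, and power for the adjusted coefficient is Φ(3.242·ratio − 1.960) plus the small opposite tail.

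| s | ratio, λ = 0.8 | power | ratio, λ = 0.9 | power |
|---|---|---|---|---|
| 10% | 0.92 | 0.85 | 0.91 | 0.84 |
| 25% | 0.80 | 0.74 | 0.775 | 0.71 |
| 50% | 0.60 | 0.49 | 0.55 | 0.43 |
| 100% | 0.20 | 0.10 | 0.10 | 0.06 |

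**4. Shared causes.** Let k be the covariance of PAM and outcome from a common cause: adjusted = total − a·(b + k)·λ. Take total = 0.20 SD (the minimally important difference in the PROMIS section) and assume a = 0.30 SD, s = 0.25, λ = 0.8. Then b = 0.25 × 0.20 / 0.30 = 0.167.

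- k = 0: 0.20 − 0.30 × 0.167 × 0.8 = 0.16, ratio 0.80.
- k = +0.25: 0.20 − 0.30 × 0.417 × 0.8 = 0.10, ratio 0.50.
- k = −0.25: 0.20 + 0.30 × 0.083 × 0.8 = 0.22, ratio 1.10.

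**5. Simulation check.** Settings were 16 practices of 69 patients, ICC 0.02, PAM without measurement error and a = 0.3. Values are in SD units.

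| True total | b | Model without PAM | PAM-adjusted | PAM-adjusted, with a positive shared cause |
|---|---|---|---|---|
| 0.30 | 0.3 | 0.30 | 0.21 | 0.15 |
| 0.30 | 0.5 | 0.30 | 0.16 | 0.07 |
| 0.15 (all through PAM) | 0.5 | 0.15 | 0.00 | −0.07 |

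With the shared cause added, the model without PAM still recovers the true total to within about 0.01.

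**6. Sample.** The plan's own yield reproduces: 4,368 × 0.97 × 0.50 × 0.65 × 0.80 = 1,101.6, or 69 per practice. Unless PAM is imputed, a model needing wave 1 PAM is limited to 4,368 × 0.97 × 0.50 = 2,118 patients, or 132 per practice. EHR data are expected for most of the 273 sampled per practice. Patient Selection asks for 140 per practice for change in systolic pressure. At the standard deviations implied by that figure (14.2 at ICC 0.01, 11.3 at ICC 0.02, alpha 0.05 assumed), power at 132 is 0.89 to 0.90, so this restriction alone costs almost no power.

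**The case against.** The strongest reply is that the two stages form a path analysis that fits the logic model, so the total can be rebuilt as direct + a·b. This is right for linear models on the same patients and covariates. The plan never says it will do so, and the identity is not exact for the percent-controlled measures in Clinical Measures if they are fitted with a non-linear link. The plan does not name a link, so that second point is conditional. The first is not.

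A second reply is that the Aim 1 text, before the two stages, promises a cross-sectional look at PA&E against teamwork and patient survey results. That is a lead-in without a model or adjustment set, and it does not reach the EHR measures.

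A third is that the equations are called simplified. The accompanying sentence lists PAM as well, so simplification does not explain its presence.

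It is also fair to say that Aims 2 and 4 need PAM for their own questions. They are not in error on this account; they only show that the gap is not filled elsewhere.

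On size, the objections largely stand. The mediated share, a and k are assumed. The 90% comes from a different analysis. At a 100% share, b would be 0.20 / 0.30 = 0.67, so adjusting for PAM should reduce residual error, and the tabulated power is somewhat low at high shares. The 1.10 ratio rests on the formula alone. The 69 per practice concerns Aim 4, not Aim 1.

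PAM timing is a separate inconsistency: months 7-12 in the Research Plan, Table 3 and Sources of Materials, but months 0-3 in the UC Berkeley human-subjects section. An early PAM score would not rescue Aim 1, because practices are classified on activities already in place.

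**Conclusion.** The concern holds, and the plan should be changed before analysis. The study's central question is an overall high-versus-low comparison. The specified Aim 1 models estimate a different quantity, the PA&E association conditional on a variable that the plan treats as its consequence. This follows from the text alone and needs no numerical assumption.

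The size cannot be fixed from the documents. Under the stated assumptions, power for the reported coefficient runs from 0.85 at a 10% mediated share to between 0.06 and 0.10 under full mediation, against 0.90 for the total. Without confounding, the coefficient is pulled toward zero if the posited mechanism holds. Shared causes of PAM and outcome can deepen or reverse that.

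Because practices are not randomised, the contrast without PAM is the descriptive comparison that Aim 1 asks for. It is not automatically an unconfounded effect.

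**What to change.** - **Primary Aim 1 model.** For each outcome: Outcome = high/low PA&E + practice size + casemix, with a practice random effect and no PAM.
- **Secondary analysis.** Keep the existing PAM-adjusted equations, labelled as direct-effect or mediation analyses, and state the no-confounding assumption they need. State which of the two models Aim 3 compares across waves.
- **Sample for clinical outcomes.** Dropping PAM removes one reason to restrict to survey respondents, but educational attainment, a candidate casemix factor, also comes from the survey. Patient Demographics names only two items from the ACOs: "We will supplement these survey data with information about patient age and sex from ACO clinical and sociodemographic data". Either limit casemix for EHR outcomes to ACO-supplied variables, or treat survey-only items as missing data for non-respondents, and say which.
- **PAM timing.** Reconcile months 7-12 with months 0-3.

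The cost is SAP wording and one extra model per outcome. No new data are needed.
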